1. PROTOCOL SUMMARY

1.1 Schedule of activities (SoA)

The procedures for the screening and treatment periods in this study are presented in Table 1 and Table 2, and the procedures for the follow-up period are presented in Table 2. Patients who continue beyond Cycle 13 will continue with all Cycle 13 assessments until termination of treatment (Table 1).

Whenever vital signs and blood draws are scheduled for the same nominal time, the assessments should occur in the following order: vital signs and then blood draws. The timing of the vital signs assessments should be such that it allows the blood draw to occur at the timepoints indicated in the SoAs. Whenever electrocardiograms (ECGs), vital signs, and blood draws are scheduled for the same nominal time, the assessments should occur in the following order: ECG, vital signs, and then blood draws. The timing of the first 2 assessments should be such that it allows the blood draw to occur at the timepoints indicated in the SoAs.

For durvalumab

- Patients may delay dosing under certain circumstances.
 - Dosing may be delayed per the Dosing Modification and Toxicity Management Guidelines, due to either an immune or a non-immune-related AE.
 - If dosing must be delayed for reasons other than treatment-related toxicity, dosing will resume as soon as feasible.
 - Dosing intervals of subsequent cycles (during chemotherapy interval is 21 days, post chemotherapy interval is 28 days) may be adapted +/-3 days as clinically feasible in order to gradually align treatment cycles with the schedule of tumor efficacy (RECIST) and PRO assessments.

For EP treatment

- Patients may delay and subsequently resume dosing per local standard clinical practice.
 - If dosing must be delayed for reasons other than treatment-related toxicity, dosing will occur as soon as feasible.

Table 1 Schedule of assessments for durvalumab therapy treatment

		During Chemotherapy 1 cycle = 21 days				Post-Chemotherapy 1 cycle = 28 days				
	Screening	C1	C2	C3	C4-C6	C5-C7 to PD		End of treatment		
Week	-4 to -1	0	Q3w ±3 days during chemotherapy and q4w ±3 days post-chemotherapy, unless dosing needs to be held for toxicity reasons							
Day	-28 to -1	1 ^a	Q21days ±3 days during chemotherapy and q28days ±3 days post-chemotherapy, unless dosing needs to be held for toxicity reasons							For details, see Section
Informed Consent										
Informed consent: study procedures ^b	X								5.1	
Consent: sample for biomarker analysis (optional)	X								5.1	
Study procedures										
Physical exam (full)	X								8.2.2	
Targeted physical exam (based on symptoms)		X	X	X	X	X		X	8.2.2	
Vital signs ^c	X	X	X	X	X	X		X	8.2.3	
ECG ^d	X	As clinically indicated							8.2.4	
Concomitant medications	<----->								6.4	
Demography, including baseline characteristics and tobacco use	X								5.1	
Eligibility criteria	X								5.1, 5.2	
Laboratory Assessments										
Clinical chemistry ^e	X	X ^f	X	X	X	X		X	Table 8	
Hematology ^e	X	X ^f	X	X	X	X		X	Table 9	
TSH ^g , (reflex free T3 or free T4 ^h)	X	X	X	X	X	X		X	Table 8	
Urinalysis	X	As clinically indicated							Table 10	
Hepatitis B and C and HIV	X								8.2.1	

		During Chemotherapy 1 cycle = 21 days				Post-Chemotherapy 1 cycle = 28 days			
	Screening	C1	C2	C3	C4-C6	C5-C7 to PD	End of treatment		
Week	-4 to -1	0	Q3w ±3 days during chemotherapy and q4w ±3 days post-chemotherapy, unless dosing needs to be held for toxicity reasons						For details, see Section
Day	-28 to -1	1 ^a	Q21days ±3 days during chemotherapy and q28days ±3 days post-chemotherapy, unless dosing needs to be held for toxicity reasons						
Efficacy evaluations									
Tumor assessments (RECIST 1.1) ^q	X	On-study tumor assessments will be performed following local standard practice, but at least with a maximum interval of 12 weeks. It is recommended that on-study tumor assessments occur q9w ± 1w for the first 12-18 weeks (relative to the C1D1, during chemotherapy treatment), and then, at least with a maximum interval of 12 weeks if signs or symptoms of progression do not happen before, if it is the standard procedure at study site, until RECIST 1.1-defined radiological progression plus an additional follow-up scan 4-8 weeks later. ^s						8.1, E	

^a Every effort should be made to minimize the time between inclusion and starting treatment (ie, within 1 day of inclusion).

^b Written informed consent and any locally required privacy act document authorization must be obtained prior to performing any protocol-specific procedures, including screening/baseline evaluations. All patients will be required to provide consent to supply a sample of their tumor (archived biopsy) for entry into this study. This consent is included in the main patient ICF. Informed consent of study procedures archival tumor sample may be obtained prior to the 28-day screening window. If laboratory or imaging procedures were performed for alternate reasons prior to signing consent, these can be used for screening purposes with consent of the patient. However, all screening laboratory and imaging results must have been obtained within 28 days of inclusion.

^c Body weight is recorded at each visit along with vital signs.

^d Normal ECG basal mandatory (28 days maximum before first treatment). Other ECG will be performed under investigator criteria.

^e Serum or plasma clinical chemistry (including LFT monitoring) and hematology may be performed more frequently if clinically indicated.

^f If screening clinical chemistry and hematology assessments are performed within 3 days prior to Day 1 (first infusion day), they do not need to be repeated at Day 1.

^g If TSH is measured within 14 days prior to Day 1 (first infusion day), it does not need to be repeated at Day 1.

^h Free T3 or free T4 will only be measured if TSH is abnormal or if there is clinical suspicion of an AE related to the endocrine system.

ⁱ For women of childbearing potential only. A urine or serum pregnancy test is acceptable. Women of childbearing potential are required to have a pregnancy test within 7 days prior to the first dose of study drug and then every 3weeks during chemotherapy and every 4 weeks during durvalumab monotherapy. Pregnancy test may occur on Day 1, but results must be available and reviewed by the treating physician or Investigator prior to commencing an infusion

^k For AEs/SAEs reported during screening, additional information such as medical history and concomitant medications may be needed

^l Results for LFTs, electrolytes, full blood count (during chemotherapy) and creatinine must be available before commencing an infusion (within 3 days) and reviewed by the treating physician or Investigator prior to dosing.

ⁿ Durvalumab is infused first followed by the etoposide + cisplatin/carboplatin regimen

^o Etoposide should be infused as local clinical practice, usually over 0.5 to 1 hour.

^p Cisplatin and carboplatin should be infused as local clinical practice. If cisplatin, usually over 1 to 2 hours. If carboplatin, usually over 0.5 to 1 hour.

^q See Section 6.1.3, Section 8.1, and E for additional details relevant to image acquisition, RECIST 1.1 assessments, and evaluation of scans after RECIST 1.1-defined progression.

^r For the PRO collection, the research nurse or study coordinator should ensure that the patient completes the questionnaire prior to any other study procedures and before discussion of PD to avoid introducing bias to the patient's responses to the questions. The EORTC QLQ-C30 should always be completed prior to the EORTC QLQLC13 module.

■ [REDACTED]

■ [REDACTED]

^t The site should complete the hospital resource use form at every scheduled and unscheduled clinic visit up to and including the study treatment discontinuation follow-up visit. If the patient discontinues study treatment for reasons other than RECIST 1.1 assessed PD, the hospital resource use form should continue to be completed until PD has been confirmed.

Note: All assessments on treatment days are to be performed prior to infusion, unless otherwise indicated.

C Cycle; ECG Electrocardiogram; IM Intramuscular; LFT Liver function test; qXw Every X weeks; qXdays Every X days; T₃ Triiodothyronine; T₄ Thyroxine; TSH Thyroid-stimulating hormone.

Table 2 Schedule of assessments for patients who have discontinued treatment with durvalumab + EP therapy

Evaluation	Time since last dose of IP								For details, see Section
	Day (±3)	Months (±1 week)						12 months and every 6 months (±2 weeks)	
	30	2	3	4	6	8	10		
Physical examination (full)	X								8.2.2
Vital signs (temperature, respiratory rate, blood pressure, and pulse)	X								8.2.3
Weight	X	X	X						8.2.3
Pregnancy test ^a	X	As clinically indicated							8.2.1
AE/SAE assessment	X	X	X						8.3
Concomitant medications	X	X	X						6.4
WHO/ECOG performance status	At timepoints consistent with tumor assessments; at 30, 60, and 90 days; and then at initiation of subsequent anticancer therapy ^b								8.2.6
Subsequent anticancer therapy ^c	←----->								8.1
Survival status ^f		X	X	X	X	X	X	X (every 2 months)	8.1
Hematology	X	X	X						Table 9
Clinical chemistry	X	X	X						Table 8
TSH (reflex free T3 or free T4 ^g)	X	X	X						Table 8
Tumor assessment (RECIST 1.1) ⁱ	On-study tumor assessments will be performed following local standard practice, but at least with a maximum interval of 12 weeks, until RECIST 1.1-defined radiological progression plus an additional follow-up scan 4-8 weeks later. ^g								8.1

^a For women of childbearing potential only. A urine or serum pregnancy test is acceptable.

^b WHO/ECOG performance status should also be collected at other site visits that the patient attends, if appropriate site staff are available to collect such information. In addition, WHO/ECOG performance status should be provided when information on subsequent anticancer therapy is provided, where possible.

^c Details of any treatment for ES-SCLC (including surgery) post the last dose of IP must be recorded in the eCRF. At minimum, collect the start date and description of the subsequent anticancer therapy.

^f Patients may be contacted in the week following data cutoffs to confirm survival status. Details of any treatment for ES-SCLC (including surgery) post the last dose of IP must be recorded in the eCRF.

^g Free T3 or free T4 will only be measured if TSH is abnormal or if there is clinical suspicion of an AE related to the endocrine system.

ⁱ See Section 6.1.3, Section 8.1, and E for additional details relevant to image acquisition, RECIST 1.1 assessments, and evaluation of scans after RECIST 1.1-defined progression.

NA Not applicable; qXw Every X weeks; T3 Triiodothyronine; T4 Thyroxine; TSH Thyroid-stimulating hormone.

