8.2.7 Patient reported outcomes (PRO)

–PRO” is an umbrella term referring to all outcomes and symptoms that are directly reported by the patient. PROs have become a significant endpoint when evaluating effectiveness of treatments in clinical studies. The following PROs will be administered in this study: EORTC QLQ-C30 v3 (core questionnaire), EORTC QLQ-LC13 (lung cancer module), patient-reported outcomes version of the CTCAE (PRO-CTCAE). (see [Appendix H and I](#)).

The PRO instruments will be completed by the patients using a paper format questionnaire on day 1 of every cycle. All assessments should be completed without assistance from anyone according to the assessment schedules. It takes approximately 30 minutes for patients to complete the questionnaires; therefore, the burden to the patient is moderate.

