8.2.7.4 Administration of the patient-reported outcome questionnaires

Patients will complete the PRO assessments in paper format during clinic visits. Each center must allocate the responsibility for the administration of the PRO instruments to a specific individual (eg, a research nurse or study coordinator) and, if possible, assign a back-up person to cover if that individual is absent. The PRO questionnaires must be administered and completed at the clinic as per the schedule of assessments. The PRO questionnaires will be administered on the days specified in the schedules of assessments. The EORTC QLQ-C30 should always be completed prior to the EORTC QLQ-LC13 module.

It is important that the significance and relevance of the data are explained carefully to participating patients so that they are motivated to comply with data collection. The following best practice guidelines should be followed when collecting PRO data:

- It is preferred that PRO questionnaires are completed prior to any other study procedures (following informed consent) and before discussion of disease progression to avoid biasing the patient’s responses to the questions.

- PRO questionnaires must be completed in private by the patient.
- Patients should be given sufficient time to complete the PRO questionnaires at their own speed.
- The research nurse or appointed site staff should stress that the information is confidential. Therefore, if the patient has any medical problems, he/she should discuss them with the doctor or research nurse separately from the ePRO assessment.
- The research nurse or appointed site staff must train the patient on how to complete the questionnaires. The research nurse or appointed site staff must remind patients that there are no right or wrong answers and avoid introducing bias by not clarifying items. The patient should not receive help from relatives, friends, or clinic staff to answer the PRO questionnaires.

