For each of the symptoms scales/items in the EORTC QLQ-C30 questionnaire, time to symptom deterioration will be defined as the time from start of study drug until the date of the first clinically meaningful symptom deterioration (an increase in the score from baseline of ≥ 10 points) that is confirmed at the subsequent assessment (at least 14 days apart) or death (by any cause) in the absence of a clinically meaningful symptom deterioration, regardless of whether the patient withdraws from study drug or receives another anticancer therapy prior to symptom deterioration. Death will be included as an event only if the death occurs within 2 visits of the last PRO assessment where the symptom change could be evaluated.

Patients with a single deterioration and no further assessments will be treated as deteriorated in the analysis. Patients whose symptoms (as measured by EORTC QLQ-C30) have not shown a clinically meaningful deterioration and who are alive at the time of the analysis will be censored at the time of their last PRO assessment where the symptom could be evaluated. Also, if symptoms deteriorate after 2 or more missed PRO assessment visits or the patient dies after 2 or more missed PRO

assessment visits, the patient will be censored at the time of the last PRO assessment where the symptom could be evaluated. If a patient has no evaluable visits or does not have baseline data, he/she will be censored at Day 1.

The analysis of time to symptom deterioration will be done with a subset of patients who have baseline scores of ≤ 90 .

Time to quality of life/function deterioration

For QoL, time to deterioration will be defined as the time from start of study drug until the date of the first clinically meaningful deterioration (a decrease in the function scales or the global health status/QoL from baseline of ≥ 10 points) that is confirmed at the subsequent assessment (at least 14 days apart) or death (by any cause) in the absence of a clinically meaningful deterioration, regardless of whether the patient withdraws from study drug or receives another anticancer therapy prior to QoL/function deterioration. Death will be included as an event only if the death occurs within 2 visits of the last PRO assessment where the QoL/function change could be evaluated.

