- Time to symptom deterioration: defined as the time from start of study drug until the date of the first clinically meaningful symptom deterioration (a decrease in the score from baseline of  $\geq 10$  points) that is confirmed at the subsequent assessment (at least 14 days apart) or death (by any cause) in the absence of a clinically meaningful symptom deterioration, regardless of whether the patient withdraws from study drug or receives another anticancer therapy prior to symptom deterioration. Death will be included as an event only if the death occurs within 2 visits of the last PRO assessment where the symptom change could be evaluated.  
Patients whose QoL (as measured by EORTC QLQ-C30) have not shown a clinically meaningful deterioration and who are alive at the time of the analysis will be censored at the time of their last PRO assessment where the QoL/function could be evaluated. Also, if QoL deteriorates after 2 or more missed PRO assessment visits or the patient dies after 2 or more missed PRO assessment visits, the patient will be censored at the time of the last PRO assessment where QoL/function could be evaluated. If a patient has no evaluable visits or does not have baseline data, he/she will be censored at Day 1.
- Time to quality of life/ function deterioration: defined as the time from start of study drug until the date of the first clinically meaningful deterioration (a decrease in the function scales or the global health status/QoL from baseline of  $\geq 10$  points) that is confirmed at the subsequent assessment (at least 14 days apart) or death (by any cause) in the absence of a clinically meaningful deterioration, regardless of whether the patient withdraws from study drug or receives another anticancer therapy prior to QoL/function deterioration. Death will be included as an event only if the death occurs within 2 visits of the last PRO assessment where the QoL/function change could be evaluated.
- Symptom improvement rate: defined as the number (%) of patients with 2 consecutive assessments at least 14 days apart that show a clinically meaningful improvement (an increase from baseline score  $\geq 10$  points for EORTC QLQ-C30 symptom scales/items) in that symptom from baseline.

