#### Endpoints analyzed:

- Change from baseline in European Organisation for Research and Treatment of Cancer Quality of Life Questionnaire Core 30 items (EORTC QLQ-C30) and Questionnaire-Lung Cancer 13 (EORTC QLQLC13):

Scores for the QLQ-C30 and QLQ-LC13 questionnaires will be calculated according to published scoring manuals or the developer's guidelines. Raw scores from scales in both questionnaires will be standardized by linear transformation so that they range from 0 to 100. Higher scores for symptom items indicate greater symptom severity, while higher scores for function and global health status/QoL items indicate better function and health status/QoL. For both questionnaires, a clinically meaningful change will be prespecified as an absolute change in score from baseline of  $\geq 10$  points (either deterioration or improvement). For the five key disease-related symptoms (cough, dyspnea, and chest pain [QLQ-LC13], and fatigue and appetite loss [QLQ-C30]), changes at each visit from baseline to disease progression or end of follow-up (whichever came first) will be analyzed using a mixed model for repeated measures (MMRM) to derive an overall adjusted mean change from baseline, reflecting the average treatment effect over visits. The model assumes PROs will be collected at multiple visits per

patient. Visits with >75% missing data will be excluded from the analysis. The MMRM included treatment, age at baseline (<65 vs ≥65 years), sex, smoking history (smoker vs non-smoker) and visit interaction as fixed factors, and baseline score as a covariate; the model further adjusted for baseline score-by-visit interaction.

Summaries of original and change from baseline values of each symptom scale/item, the global HRQoL score, and each functional domain will be reported by visit.

Time to symptom deterioration and time to quality of life / function deterioration (defined in 4.2.2) will be analyzed by product limit methods to provide summaries of the number and percentage of patients experiencing a clinically meaningful deterioration or death, the median time to deterioration together with the corresponding 95% CIs, as well as the Kaplan-Meier plot. An stratified log-rank test adjusted for therapy will be used with HR s and 95% CIs calculated using a stratified Cox proportional hazards model.

Symptom improvement rate and Quality of life / function improvement (defined in 4.2.2) will be summarized.

- Changes from baseline in PRO-CTCAE:

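### Time to PRO deterioration is defined past treatment withdrawal, but the only stated questionnaire timing is Day 1 of each cycle, so censoring at treatment stop is likely to be informative

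*Protocol*

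**What the plan says.** **Endpoint.** Protocol 9.5.2.3 runs time to symptom deterioration "regardless of whether the patient withdraws from study drug or receives another anticancer therapy prior to symptom deterioration", and Protocol 9.4 has the same clause. SAP 4.2.2.2 repeats it, for QoL/function as "regardless of whether the patient withdraws from study drug or receives another anticancer therapy prior to QoL/function deterioration".

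**Collection.** Protocol 8.2.7: "The PRO instruments will be completed by the patients using a paper format questionnaire on day 1 of every cycle". Protocol 8.2.7.4: "The PRO questionnaires will be administered on the days specified in the schedules of assessments". Protocol 1.1 assigns the follow-up period to Table 2, "Schedule of assessments for patients who have discontinued treatment with durvalumab + EP therapy". As available, that table lists examinations, laboratory tests, adverse events, performance status, survival and tumor assessment, but no questionnaire.

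**Censoring.** Patients alive without deterioration are censored at their last evaluable PRO. On deaths, both documents say: "Death will be included as an event only if the death occurs within 2 visits of the last PRO assessment". For QLQ-C30 symptoms, the Protocol also counts a single deterioration with no later assessment as an event. The SAP does not carry that rule over.

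**Mixed model.** SAP 5.2.2 analyzes change in five key symptoms from baseline to progression or end of follow-up, whichever is earlier. SAP 6.2 foresees no method for missing data beyond scoring partly completed subscales.

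**The concern.** The definition asks a question that the stated collection cannot answer. Patients leave treatment largely because of progression, clinical deterioration or toxicity, which is when symptoms are likely to worsen. If questionnaires end with the cycles, a patient who has not yet deteriorated is censored just as the risk changes. Kaplan-Meier then treats that patient as exchangeable with those still on treatment. The curve describes something close to symptoms while treated, under a label that says withdrawal makes no difference.

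Protocol 2.1 gives understanding whether delayed progression is meaningful to patients as a reason for measuring HRQoL. The period around and after progression therefore matters to the study's own rationale.

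**Working it through.** The documents give no expected event count or precision for the PRO endpoints, so there is no planned figure to reproduce. The check has two parts.

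**1. The passages side by side, for a patient who stops treatment**

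| Situation | Treatment in the analysis |
|---|---|
| Confirmed deterioration before stopping | Event |
| Deterioration first seen at the last questionnaire | Event under the Protocol's QLQ-C30 symptom rule; under the SAP as written it cannot be confirmed |
| Death within 2 visits of the last PRO | Event, although a visit is undefined once none is scheduled |
| Treated through progression (6.1.3) | Cycles and questionnaires continue |
| None of the above | Censored at the last PRO |

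The mixed model ends at progression by design. It loses data only for patients who stop before progression, for example for toxicity.

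**2. Illustrative simulation of the last row**

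Inputs from the documents:
- Median time to progression of 4 to 6 months (Protocol 2.3.3), used as a stand-in for time to treatment stop.
- Median OS of 13.0 months (Protocol 2.3.1.2). The runs below gave 13.5 to 14.3.

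Assumptions not in the documents:
- On-treatment median to deterioration of 6 or 9 months.
- Deterioration hazard after stopping multiplied by k = 1, 2 or 4.
- Exponential times, with deaths only after stopping.
- Two visits taken as 56 days, and cut-off at 18 months.
- No confirmation requirement.

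With on-treatment hazard h = ln 2 / median, the hazard is h up to the stop and k × h afterwards. Visits are every 3 weeks to day 84, then every 4 weeks. Collection as planned ends at the last visit before the stop. The comparison continues four-weekly questionnaires to death. There were 40,000 patients per scenario. Each range covers stop medians of 4, 5 and 6 months; the 12-month columns also cover both deterioration medians.

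| k | 12-month deterioration-free, as planned | Same, continued collection | Excess (points) | Median in months, planned vs continued (on-treatment median 6) | Same (on-treatment median 9) |
|---|---|---|---|---|---|
| 1 | 19–32% | 14–23% | 5–9 | 5.5 vs 5.5 | 7.4 vs 6.4–6.5 |
| 2 | 19–32% | 9–19% | 9–14 | 5.5 vs 4.6 | 7.4 vs 5.5–6.4 |
| 4 | 19–33% | 5–15% | 12–20 | 5.5 vs 3.7–4.6 | 7.4 vs 4.6–5.5 |

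The excess is taken scenario by scenario (k = 2, stop median 4, on-treatment median 9: 30% − 16% = 14 points). After stopping, 43% to 62% of patients are censored: 0.43 × 85 ≈ 37 to 0.62 × 85 ≈ 53 patients. A further 8% to 9% are events through death within 56 days. Medians fall on visit dates, so they move in steps. An excess remains at k = 1 because later deaths go uncounted.

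**Sensitivity to set-up.** A 28-day grid throughout, with OS tuned to 13 months, gives 2–4 points with no rise and 7–14 points with a two- to threefold rise. The 3-then-4-week grid with a two- to threefold rise gives 9–17 points. On that last set-up, applying the SAP's confirmation requirement literally moves the planned 12-month estimate from 18–31% to 22–33%.

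**The case against.** A reader might infer that Table 2 proves that no questionnaire is given after stopping. It does not:
- Its footnotes are imperfect. Letters d, e and h are absent, and the tumor row carries g, which is a thyroid note.
- It has no row for the hospital resource form, which a Table 1 footnote continues after discontinuation.
- Table 1's own PRO row is missing from the available text, so an end-of-treatment questionnaire cannot be excluded. It would add at most one point.
- Section 1.1 speaks of aligning cycles with a schedule of PRO assessments, and 7.1.1 says that data collection continues per protocol after discontinuation.

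These points stand, so the main evidence is the sentence in 8.2.7. None of the other passages names a questionnaire after treatment. The Table 1 footnote on PROs has no extension past discontinuation, unlike the resource-form footnote.

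A reader might also infer that everyone who stops is censored, or that the mixed model is generally undermined. The exceptions tabulated above rule out both.

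On importance, the study is single-arm and descriptive, and Table 3 lists change from baseline as the PRO endpoint. Section 9.5.2.3 has QLQ-C30 time to deterioration summarized only where feasible, though it also prespecifies deterioration in key symptoms. The Kaplan-Meier standard error at 12 months with 85 patients is about 6 to 9 points, so much of the illustrated excess lies within sampling error. Unlike sampling error, it does not shrink with more patients.

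**Conclusion.** The concern holds as a mismatch between the endpoint definition and the stated collection times. Among patients who stop without an earlier deterioration and do not die soon afterwards, censoring is likely to be informative, and the expected error is towards later deterioration. That direction assumes that deterioration or death is at least as frequent after stopping as before. Relief of toxicity symptoms after stopping would work against it.

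The size is illustrative: a few points at 12 months with no rise in hazard, and roughly 7 to 17 points with a two- to threefold rise. A reader might take these as estimates of the bias in this trial, which the documents cannot support. The time to progression comes from their account of chemotherapy alone, and neither the deterioration medians nor the hazard multiples appear in them. The primary safety endpoints are unaffected. The point deserves correction because it concerns what a prespecified secondary analysis claims to measure, and correction is cheap.

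**What to change.** **Preferred: reconcile 8.2.7, Table 2 and the endpoint definition.**
- Add QLQ-C30 and QLQ-LC13 to Table 2 at the existing Day 30, month 2 and month 3 visits, and extend 8.2.7 to match. PRO-CTCAE has no time-to-deterioration analysis, so this point does not require it.
- State in 9.4, 9.5.2.3 and SAP 4.2.2.2 that deterioration is observed only up to the month 3 follow-up visit, and say what within 2 visits means after treatment ends.
- Carry the Protocol's single-deterioration rule into the SAP.

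Cost: up to three extra questionnaire sets per patient at visits already scheduled. Section 8.2.7 puts completion at about 30 minutes. Return will be incomplete and some bias remains after month 3: about 0.5 to 4 points at 12 months in the illustration, where the 2–4 point figures for a two- to threefold rise assume complete return. Censoring there falls from 44–62% to 12–31%.

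**Otherwise, wording only.** Delete the clause about withdrawal from study drug in 9.4, 9.5.2.3 and SAP 4.2.2.2, label the endpoints on-treatment, and report the number censored by reason for stopping. This needs no new data. It corrects the claim but does not recover symptoms after treatment.
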